## 4.6 Recruit WIC Participants

[figure not shown]
Over a 5 month period beginning in January 2013 Westat will screen about 98 new WIC enrollees at each of 80 selected WIC service sites during a pre-determined enrollment period. The new enrollees will include prenatal mothers and postnatal infants <2.5 months old (whose mothers were not enrolled prenatally) who are enrolled at the service site or at outreach locations (hospital, mall, satellite sites) by staff in the service site. We expect to recruit about 55.4 new enrollees per site. The 80 WIC sites will be of varying sizes and therefore have vastly different enrollment flows (from 1.5 new enrollees per day up to 14 or more new enrollees per day). To accommodate the differences in enrollment flow the recruitment window at each site will range from 7 to 66 days (about 1 to 13 weeks). The enrollment start dates will be staggered and slightly frontloaded to ensure the sites with longer windows begin enrollment early in the period. Details of the sampling process can be found in the Final Sampling Plan in Deliverable 8b, submitted to FNS on February 17, 2012. Following is a description of our process for recruiting and training Westat staff, and a discussion of the steps in recruiting new WIC enrollees into the ITFPS-2.

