### 4.6.3 Recruitment and Enrollment Steps

Participant enrollment at the service site is presented in Figure 4.5, and described below.

1. **Identify Eligible WIC Enrollees.** WIC staff will identify all pregnant women in the designated study enrollment window who are enrolling in WIC for the first time for their current pregnancy and all infants less than 2.5 months whose mothers did not enroll prenatally. They will complete a 2-ply referral form that includes WIC ID, name, contact information, pregnancy status, age, and language. One copy will go to the woman (yellow); the other will be saved for the Westat recruiter/helper who will collect the forms at the end of the day.
2. **Intercept on site.** The Westat recruiter/helper will look for women holding a yellow referral form and attempt to intercept her at the end of her WIC visit in order to introduce the study and screen the woman. Barring that, they will make sure the woman gets a study flyer with a toll-free number she can call to learn more about the study. Barring that, they will make sure the woman gets a study flyer with a toll-free number she can call to learn more about the study.
3. **Introduce Study.** A Westat recruiter/helper will take the woman to a private space (designated for the ITFPS-2 recruitment activity by the site) and introduce the study. This will involve providing the woman with a study flyer that explains what participation in the study entails, the incentives, and how the mother can play an important role in understanding the health of all infants by joining the study. If a woman expresses interest in participating in the study but does not have time to go through the recruitment process, the recruiter/helper will obtain contact information and a Westat telephone recruiter will contact her to introduce the study and determine whether she is eligible.
4. **Assign to Core or Supplemental Sample.** The screener instrument will be programmed to assign participants to either the core or supplemental group in an alternating pattern. For sampling purposes it is necessary to assign a woman to one of these groups before we screen her. (See Sampling Plan, Deliverable 8 for details). In sites that have a Westat field recruiter, the recruiter will assign interested new enrollees to the core or supplemental sample using a laptop; in sites where a Westat helper has

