### Core Sample

The Horvitz-Thompson core-sample weight for an infant will be

$$W_{Bijk} = \frac{52}{22} \frac{M_i}{4M_{ij}} \frac{E_i}{2} \frac{C_{ij}}{D_{ij}} \frac{22L_{ij}}{L_{ij}} \frac{N_{ij}}{n_{ij}},$$

where the first factor adjusts for the fact that the field period contains only 22 of the 52 weeks in a year,,  $M_i$  is the count of new enrollments in the  $i$ -th stratum according to the PC2010,  $M_{ij}$  is the count of new enrollments (defined the same way from the same source) in the  $j$ -th first-stage sampling unit in  $i$ -th stratum, the 4 in the denominator adjusts for the fact of sampling four first-stage sampling units per stratum in the first phase of selection,  $E_{ij}$  is the number of eligible first-stage units among the 4 sampled in the  $i$ -th stratum, the 2 in the denominator accounts for the fact that 2 first-stage units will be selected in the second phase among the  $E_i$  eligible,  $C_{ij}$  is the count of clients in same first-stage sampling unit according to local reports at the time of first-stage sampling unit scouting,  $D_{ij}$  is the count of clients in the sampled service site within the  $j$ -th first-stage sampling unit in  $i$ -th stratum according to the same local reports, 22 is the length of the field period in weeks,  $L_{ij}$  is the length of the window in days,  $N_{ij}$  is the number of new enrollees during the window, and  $n_{ij}$  is the number of clients who are recruited into the evaluation study

 All newly enrolled pregnant women in April of 2010 plus 20 percent of newly enrolled infants. All from the PC2010.

 It is not necessary to define clients here as new enrollments although that would be best if possible. Of course, it is important to use whatever was used for sampling.

 New enrollees here means pregnant women enrolling for the first time during the current pregnancy plus new infant enrollees whose mothers appear not to have been on WIC during the gestation of the infant.

during the window. Here it is important to note that  $n_{ij}$  counts those who give informed consent and not just those who pass the screening test of not having previously enrolled for WIC during the current pregnancy or the pregnancy leading to the birth of the infant being enrolled.

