Although this formula appears complex, we hope that the weights will have low variation. Various simplifications will come into play in different situations. For a given sampled service site, if the entries on the PC2010 identify the service site (rather than a composite site), the service site will have been sampled at the first stage of selection and no second stage of service site selection will have been needed; in this case we will have  $\frac{C_{ij}}{D_{ij}} = 1$ . Even when the second stage of service site

selection is needed, as long as the enrollment figures provided for second-stage selection are highly accurate,  $\text{corr}(M_{ij}, C_{ij})$  should be large and therefore the ratio  $\frac{C_{ij}}{M_{ij}}$  should be close to 1. If the

PC2010 data or the local scouting data turn out to be inaccurate, weights will vary more. On average, we expect the weights to be on the order of 550. This is based on an assumption of two million new enrollees in a year, 78 percent coverage, and a recruited sample size for the core sample of 2804.

Of course, to the extent that there is bad information at any phase or that there is a shift in site operations that reduces the predictive value of past data, the weights will vary. This is a concern because highly variable weights reduce the precision of survey estimates, and there is the potential for the cases with large outlying weights to have undue influence on estimates. Note that these weights will be constant within service site but vary across service sites. If there are isolated incidences of sites with weights much larger than the predicted average of 550, we will consider trimming the weights to avoid the situation where the results from such an office dominate the national estimates on a weighted basis. We are hopeful that this will not be required, but will carefully check for the possibility and take appropriate steps if the condition is detected.

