The key to effective nonresponse adjustments is the availability of good auxiliary variables to be used in the adjustment. The adjustment for those who initially consent but do not respond to the initial (prenatal or 1-month) interview is most limited in this regard. We will ask the service sites to provide a few key pieces of information about each potentially eligible WIC enrollee for use in nonresponse adjustment, including WIC ID; whether the enrollment was prenatal or postnatal; age; language; and income. In addition, the recruiter/helper will determine, with the help of the site, whether an enrollee refused a study flyer.

Also, we will build models of attrition at each wave based on the data collected to date. Various modeling methods could be considered, and these methods have been found to work approximately equally well (Folsom and Witt, 1994; Rizzo, Kalton, and Brick, 1996; Judkins, et al 2005); the real question is which variables to allow into the modeling and how to deal with missing data in the early wave data.

In many surveys, one step (generally the final step) in the sequence of weighting adjustments is to calibrate the weights (e.g., using poststratification or raking adjustments) to control totals from trusted sources, such as census totals or estimates from administrative record systems or larger surveys. In this case, no such trusted source exists, so this calibration step will not be possible.

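### The core base weight corrects for non-recruitment with one ratio per site, and no stated step applies the enrollee data that sites supply to women who do not consent

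*Combined protocol and SAP*

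**What the plan says.** Section 6.2 (Core Sample) builds the base weight as a product of selection factors and a last factor N_ij/n_ij. N_ij is the number of new enrollees at the site during the window. The plan says that n_ij "counts those who give informed consent and not just those who pass the screening test". It then adds: "Note that these weights will be constant within service site but vary across service sites". The combined-sample weight is this weight multiplied by 1/(1+r), so it inherits the same factor.

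The opening of Section 6.2 describes the adjustments placed on top as being for nonresponse across the interviews. Section 6.3 (Weights) carries them out by giving a nonresponding case a weight of zero and moving its base weight to similar respondents in the same cell.

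On auxiliary data, Section 6.3 says: "The adjustment for those who initially consent but do not respond to the initial (prenatal or 1-month) interview is most limited in this regard". It then says that sites will supply WIC ID, prenatal or postnatal enrollment, age, language and income for each potentially eligible enrollee for nonresponse adjustment, and that recruiters will note who refused a flyer. Section 4.6.3, step 1, describes the form that WIC staff fill in for every eligible enrollee they identify: "They will complete a 2-ply referral form that includes WIC ID, name, contact information, pregnancy status, age, and language".

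**The concern.** The site ratio spreads the weight of every woman who is not recruited equally over the consenters at her site. If postnatal enrollees, teenagers or Spanish speakers consent less often than others at the same site, they stay under-represented after weighting.

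The wave adjustments cannot repair this as described, because they redistribute base weights and a woman who never consented has none. Section 6.3 rules out calibration to external totals. The checks to which Section 6.4 commits compare respondents across waves, or weights with and without a wave's adjustment, and so begin with consenters. External benchmarking is only a possibility there, and the plan says it cannot isolate nonresponse.

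What is at stake is the stated aim of nearly unbiased population estimates, such as the breastfeeding initiation rate. Prenatal versus postnatal entry is a planned comparison (Section 2.4) and part of the time-in-WIC composite (Section 7.2), and mother's age is a reporting subgroup. Section 4.6.3 says consent procedures for mothers under 18 vary by State, so different consent rates by age are plausible.

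**Working it through.** **Inputs from the documents**

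- Section 4.6: "Westat will screen about 98 new WIC enrollees at each of 80 selected WIC service sites", and "We expect to recruit about 55.4 new enrollees per site" (core and supplemental together).
- Section 4.6.3, step 4: the screener is programmed to "assign participants to either the core or supplemental group in an alternating pattern", taken here as 1:1.
- Section 6.2: "a recruited sample size for the core sample of 2804", with two million new enrollees a year, 78% coverage and an average weight of about 550.

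**1. The plan's own figure.** 2,000,000 × 0.78 / 2,804 = 556.3. This agrees with about 550 (1.2% off), so 2,804 is the count on which the weights rest.

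**2. Loss between screening and recruitment.**

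- Core-assigned: 98 × 80 / 2 = 3,920, or 49 per site.
- Recruited: 2,804 / 80 = 35.05 per site.
- Recruitment rate R = 2,804 / 3,920 = 0.715, so the loss is 28.5%. It would be 27.0% with 96 screened per site and 29.9% with 100.

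**3. Size of the site ratio.** The expected N_ij/n_ij is 49 / 35.05 = 1.40 if N_ij counts core-assigned enrollees. It is 98 / 35.05 = 2.80 if N_ij counts all new enrollees, as Section 6.2 words it; that value also carries the 1-in-2 assignment to the core.

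**4. Bias that a single ratio leaves (illustration on assumptions).** Let s be the postnatal share of enrollees, g the prenatal minus postnatal consent gap, and d the outcome difference between the two groups. R = 0.715 stands in for the overall consent rate.

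- Postnatal consent: b = R − (1 − s)g.
- Postnatal share after the site ratio: s·b/R.
- Absolute bias in an overall estimate: (s − s·b/R)·d = s(1 − s)·g·d / R.

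| s | g | d | Bias (points) |
|---|---|---|---|
| 0.10 | 0.05 | 0.10 | 0.10 × 0.90 × 0.05 × 0.10 / 0.715 = 0.06 |
| 0.20 | 0.10 | 0.20 | 0.20 × 0.80 × 0.10 × 0.20 / 0.715 = 0.45 |
| 0.30 | 0.20 | 0.20 | 0.30 × 0.70 × 0.20 × 0.20 / 0.715 = 1.17 |

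In the middle row, prenatal consent is 73.5% and postnatal 63.5%, and the weighted postnatal share is 17.8% instead of 20%. A separate ratio for each of the two groups restores the 20% and removes this part of the bias.

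**5. Scale.** For a 50% estimate with n = 2,804, SE = √(0.25 × deff / 2,804). That is 0.94 points at a design effect of 1 and 1.34 points at 2 (both assumed). The bias therefore ranges from negligible to about one standard error.

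**The case against.** The best reply is that the plan does gather the right data. Section 6.3 asks for the covariates on each potentially eligible enrollee for nonresponse adjustment, and a flyer-refusal flag is informative mainly about women who decline. The statement about constant weights concerns base weights only, and the later adjustment cells do vary within site. The Sampling Plan, which is cited for detail, may contain a consent step that cannot be seen here. A wrong prenatal/postnatal mix also does not by itself bias estimates made within either group.

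Most of this stands. A reader might infer that the plan ignores these covariates altogether; Section 6.3 shows that it does not. What does not follow is that non-consent is handled. Section 6.3 attaches the data to consenters who miss the first interview, and its method moves base weight that a non-consenter does not have. Adding a further consent adjustment on top of N_ij/n_ij would count the same loss twice, so Section 6.2 would have to change if the data are to serve this purpose.

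Two other stronger readings should be resisted.

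- **That 28.5% of women refuse.** The figure also includes women found ineligible on residence plans, caregiver status or age, and women deferred to a later call and not reached. The documents do not split it, and refusals before screening may lie outside it.
- **That this is the largest single loss.** No wave attrition rate is stated. A new loss of about 3.3% at each of 10 waves would equal it, since 1 − 0.715^(1/10) = 0.033.

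**Conclusion.** The point holds in limited form. Followed as written, Section 6.2 corrects for non-recruitment with one ratio per site, and no stated step carries the covariates of Section 6.3 to women who do not consent. The loss of 28.5% assumes 1:1 assignment and 98 screened per site, and is not a refusal rate.

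The bias of about 0.06 to 1.2 points rests wholly on assumed shares and gaps, because the documents give no consent rate by prenatal/postnatal status, age or language. Its direction is unknown. A reader might conclude that every overall estimate is materially biased; the documents do not support that, since the bias vanishes where either the consent gap or the outcome gap is zero. Towards the upper end of the range it is comparable to one standard error, and a confidence interval would not reflect it. This is a cheap improvement to make before the weights are built, and it does not invalidate the design.

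**What to change.** In Section 6.2, replace the single N_ij/n_ij by a consent adjustment in these steps:

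1. Separate known ineligibles from women who refused or were not reached, and report the groups separately.
2. Form cells from prenatal/postnatal status, language and age group. Add income where it is available: Section 6.3 lists it, but the referral form in Section 4.6.3 does not.
3. Pool cells across sites or strata where they are small. With 35 core recruits per site and a postnatal share of 10 to 30%, a site has only about 3.5 to 10.5 postnatal recruits before any split by language or age.
4. Use the ratio of eligible enrollees to consenters within each cell, then ratio-adjust to the site count so that site totals are kept.
5. Repeat the step in each replicate. Section 6.5 already says that the Section 6.2 procedures are repeated for each replicate.

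Section 6.3 should then state which data serve the consent step and which serve the first-interview step. The cost is some programming and slightly more weight variation within site. The main covariates are already on the referral form.

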### Total Sample

When analyses use both the core and supplemental samples, a different set of baseweights will be required. Let  $r_{ijk}$  be the retention rate in the supplemental sample for persons in the sampling domain that contains the infant. The baseweight for the infant in the total sample will be

$W_{BTijk} = \frac{1}{1+r_{ijk}} W_{Bijk}$ . This same formula will be used whether the infant was sampled as part of the

core or as part of the supplemental sample. Note that if the infant is from a rare group that is always retained when found (such as children of black mothers), the weight for the infant in the total sample will be half the weight it receives when the core sample is analyzed by itself. At the other extreme, when an infant belongs to a common group that is never retained when found in the supplemental sample (such as children of obese Hispanic mothers), then the baseweight for the infant is the same whether the core is analyzed by itself or in combination with the supplemental sample.

### 6.3 Missing Data Compensation

Given the large number of planned interviews for each sampled mother, it is inevitable that there will be missed interviews resulting in complex missing data patterns. We will attempt to mitigate the risk of ensuing nonresponse bias by a combination of nonresponse adjustment to the sampling weights and imputation. We will prepare a separate set of weights for each wave of data collection. The only respondents that will receive a positive weight for a wave will be those who responded to the wave and those who missed the wave but returned to the sample after missing no more than two consecutive waves. Respondents returning to the sample after one or two missed waves (interviews) will be asked some retrospective “catch-up” questions to get the timing of a few critical items where transitions are noted such as when nursing mothers stopped nursing, and when cereal was introduced into the child’s diet. Imputation will be used to fill in scattered item nonresponse within completed interviews. It will also be used to fill in data from other sources such as hospital records when we have questionnaire data from mothers.

#### **Weights**

Table 6-1 shows a planned set of weights. In addition to the cross-sectional weight for each wave, we will create some longitudinal weights for analyses that require analysis of linked data across waves. We note that simple change estimates (as in the percent still breastfeeding) do not require linked data. These change estimates will be prepared by forming point estimates for each wave with

---

 Respondents get the full interview for the month in which they are doing an interview, regardless of missed interviews or which sample they are in (core or supplemental). So questions that require reporting a “date” (e.g., cessation of breastfeeding, introduction of formula, or introduction of supplemental foods) will be asked at every applicable interview until the mother gives us a date or until the question is no longer part of the interviews.

Table 6-1. Weights to be prepared and delivered

Weight name	Core only or combined?	Positive for respondents at which waves?	Additional notes
PrenatalWgt	Core only	Prenatal	
Month1CoreWgt	Core only	1-mo	Only prenatally recruited infants and infants recruited postnatally within the window for the 1-mo interview
Month1CombWgt	Combined	1-mo	Only prenatally recruited infants and infants recruited postnatally within the window for the 1-mo interview
Month3CoreWgt	Core only	3-mo	
Month5CoreWgt	Core only	5-mo	
Month7CoreWgt	Core only	7-mo	
Month7CombWgt	Combined	7-mo	
Month9CoreWgt	Core only	9-mo	
Month11CoreWgt	Core only	11-mo	
Month13CoreWgt	Core only	13-mo	
Month13CombWgt	Combined	13-mo	
Month15CoreWgt	Core only	15-mo	
Month18CoreWgt	Core only	18-mo	
Month24CoreWgt	Core only	24-mo	
Month24CombWgt	Combined	24-mo	
HazardModelCoreWgt	Core only	Prenatal + 1-mo or 3-mo if postnatally recruited	Good for modeling hazard of weaning & introduction of various foods; also good for modeling of BF initiation
HazardModelCombWgt	Combined	At least one postnatal interview	Good for modeling introduction of various foods. Earliest weight that uses entire sample. Larger sample size than HazardModelCoreWgt but can't be used in conjunction w/prenatal data.
InfantCoreLongWgt	Core only	Responded every wave from birth through 13 mo.	Good for growth curve modeling of calories/other variables measured each wave. No plans for analysis, but would be expected by many users on a RUF.

Table 6-1. Weights to be prepared and delivered (continued)

Weight name	Core only or combined?	Positive for respondents at which waves?	Additional notes
ToddCoreLongWgt	Core only	Responded every wave from birth forward	Good for growth curve modeling of calories or other variables that are measured each wave. No plans to use in our analysis, but would be expected by many users on a RUF.
CritWaveLongWgt	Combined	1/3, 7, 13, 24	If prenatally recruited or recruited postnatally within the 1-mo interview window, responded at mos. 1, 7, 13, and 24. If postnatally recruited, after the 1-mo interview window responded at mos. 3, 7, 13, and 24. Good for growth curve modeling with procedures that cannot handle missed waves.

the wave-specific cross-sectional weight and then subtracting the two estimates at the macro level to get estimates of net change.

The weighting adjustments will be fairly standard. The approach entails giving a zero weight to the nonresponding case and redistributing the base weight of the nonrespondent to responding but otherwise similar cases. This process is done within nonresponse adjustment “cells.” Nonresponse is assumed to be a perfectly random phenomenon within each cell. Once the cells have been defined, Westat has standardized software for making these adjustments that we have used very often over the last 20 years. The approach we propose to use to form the cells for nonresponse adjustment uses a class of procedures known as “doubly robust” adjustments. In contrast to traditional approaches for forming nonresponse adjustment cells, these procedures place greater emphasis on the modeling of critical outcomes in the development of cells and somewhat reduced emphasis on the modeling of nonresponse propensity. In a survey with many outcomes, the challenge is determining the key outcomes to use in this modeling exercise. For WIC ITFPS-2, we propose to develop a binary indicator at each wave for whether the mother is following recommended feeding practices for the age of the infant. We will then model this in terms of data from prior waves to obtain a set of cells that vary in maternal conformance to recommended feeding practices. We will then cross these cells with the cells defined more traditionally to predict nonresponse propensity. If we use five cells from each model, that will give us a total of 25 nonresponse adjustment cells at each wave that vary substantially in both propensity to follow recommended feeding practices and propensity for nonresponse. Adjusting for nonresponse within these cells will result in doubly robust nonresponse-

adjusted weights. Nonresponse bias will be reduced for a wide range of statistics with this approach but particularly for statistics about suboptimal feeding practices.

The key to effective nonresponse adjustments is the availability of good auxiliary variables to be used in the adjustment. The adjustment for those who initially consent but do not respond to the initial (prenatal or 1-month) interview is most limited in this regard. We will ask the service sites to provide a few key pieces of information about each potentially eligible WIC enrollee for use in nonresponse adjustment, including WIC ID; whether the enrollment was prenatal or postnatal; age; language; and income. In addition, the recruiter/helper will determine, with the help of the site, whether an enrollee refused a study flyer.

Also, we will build models of attrition at each wave based on the data collected to date. Various modeling methods could be considered, and these methods have been found to work approximately equally well (Folsom and Witt, 1994; Rizzo, Kalton, and Brick, 1996; Judkins, et al 2005); the real question is which variables to allow into the modeling and how to deal with missing data in the early wave data.

In many surveys, one step (generally the final step) in the sequence of weighting adjustments is to calibrate the weights (e.g., using poststratification or raking adjustments) to control totals from trusted sources, such as census totals or estimates from administrative record systems or larger surveys. In this case, no such trusted source exists, so this calibration step will not be possible.

